6.5 Overdose

An overdose is defined as the accidental or intentional administration of any dose of a product that is considered both excessive and medically important. All occurrences of overdose must be reported as an SAE (see Section 6.1.1 for reporting details.).

6.6 Potential Drug Induced Liver Injury (DILI)

Wherever possible, timely confirmation of initial liver-related laboratory abnormalities should occur prior to the reporting of a potential DILI event. All occurrences of potential DILIs, meeting the defined criteria, must be reported as SAEs (see Section 6.1.1. for reporting details).

Potential drug induced liver injury is defined as

ALT or AST elevation > 3 times upper limit of normal (ULN)

AND

Total bilirubin > 2 times ULN, without initial findings of cholestasis (elevated serum alkaline phosphatase),

AND

No other immediately apparent possible causes of AT elevation and hyperbilirubinemia, including, but not limited to, viral hepatitis, pre-existing chronic or acute liver disease, or the administration of other drug(s) known to be hepatotoxic.

6.7 Other Safety Considerations

Any significant worsening noted during interim or final physical examinations, electrocardiograms, x-rays, and any other potential safety assessments, whether or not these procedures are required by the protocol, should also be recorded as a nonserious or serious AE, as appropriate, and reported accordingly.

7 DATA MONITORING COMMITTEE AND OTHER EXTERNAL COMMITTEES

To provide independent oversight of safety, efficacy, and study conduct, a data monitoring committee (DMC) will be instituted. The DMC will meet regularly to ensure that subject safety is carefully monitored. The DMC will convene additional ad hoc meetings if necessary. Following each meeting, the DMC will recommend continuation, modification, or discontinuation of the study based on observed toxicities. The DMC will also review the interim analysis results and determine whether stopping criteria for superiority are met at that time. A separate DMC charter will describe the activities of this committee in more detail.

8 STATISTICAL CONSIDERATIONS

8.1 Sample Size Determination

The sample size is calculated in order to compare the overall survival (OS) between subjects randomized to receive nivolumab and subjects randomized to receive everolimus.

Approximately 569 events (ie, deaths) with an interim analysis after 398 events (70% of total OS events needed for final analysis) provides 90% power to detect a hazard ratio (HR) of 0.76 with an overall type I error of 0.05 (two-sided). The HR of 0.76 corresponds to a 32% increase in the median OS, assuming a median OS of 14.8 months for everolimus and 19.5 months for nivolumab. The stopping boundaries at interim and final analyses will be derived based on the number of deaths using O'Brien and Fleming α spending function. It is projected that an observed hazard ratio of 0.845 or less, which corresponds to a 2.7 months or greater improvement in median OS (14.8 mo vs 17.5 mo), would result in a statistically significant improvement in OS for nivolumab at the final OS analysis.

Approximately 822 subjects will be randomized to the two arms in a 1:1 ratio. Assuming a piecewise constant accrual rate (with a maximum rate of 63 subjects/month and an average rate of 41 subjects/month), the accrual will take approximately 20 months. The total duration of the study from start of randomization to final analysis of OS is expected to be 42 months (20 months of accrual + 22 months of follow-up).

Table 8.1-1 summarizes the expected timing of each analysis.

Table 8.1-1: Schedule of Analyses		
	Interim Analysis	Final Analysis
Conditions	at least 398 OS events	569 OS events
Expected timing	30 months (20 months of accrual + 10 months of follow-up)	42 months (20 months + 22 months of follow-up)
Alpha level	Interim OS projected at 0.0148 level ^a	Final OS analysis projected at 0.0455 level ^a

^a Using O'Brien and Fleming alpha spending function in case exact 398 OS events are observed at the interim OS analysis.

8.2 Populations for Analyses

- All enrolled subjects: All subjects who signed an informed consent form and were registered into the IVRS
- All randomized subjects: All subjects who were randomized to any treatment arm in the study. This is the primary dataset for analyses of efficacy and baseline characteristics
- All treated subjects: All subjects who received any dose of nivolumab or everolimus. This is the primary dataset for dosing and safety
- PK subjects: All subjects with available serum time-concentration data from randomized subjects dosed with nivolumab
- Immunogenicity subjects: All subjects with available data from randomized subjects dosed with nivolumab
- All randomized PD-L1 measurable subjects: All randomized subjects with a measurable PD-L1 expression result (ie excludes indeterminable and unknown)
- Biomarker subjects: All subjects with available biomarker data from randomized subjects

8.3 Endpoints

The primary objective (ie, clinical benefit comparison) will be measured by the primary endpoint of overall survival as defined in Section 8.3.1.

The secondary objectives of assessment of objective response rate (ORR), progression-free survival (PFS) and duration of objective response will be measured by the secondary endpoints defined in Sections 8.3.2.1, 8.3.2.2, and 8.3.2.3.

The second secondary objective (To evaluate whether PD-L1 expression is a predictive biomarker for OS) will be measured by the same primary endpoint, ie. OS.

The secondary objective related to the safety profile of both drugs will be measured by the endpoints defined in Section 8.3.2.4.

The last secondary objective (ie, evaluation of patient-reported outcomes) will be measured by the endpoint of disease-related symptom progression rate defined in Section 8.3.2.5.

8.3.1 Primary Endpoint

Overall Survival (OS) is defined as the time from randomization to the date of death. A subject who has not died will be censored at last known alive date.

Subject status will be followed every 2 - 4 weeks while on treatment and then every 3 months.

8.3.2 Secondary Endpoints

8.3.2.1 Objective Response Rate

Objective response rate (ORR) is defined as the number of subjects with a best response of CR or PR divided by the number of randomized subjects. Best overall response (BOR) is defined as

the best response designation, as determined by the investigator, recorded between the date of randomization and the date of objectively documented progression per RECIST v1.1 or the date of subsequent therapy, whichever occurs first. For subjects without documented progression or subsequent therapy, all available response designations will contribute to the BOR determination. For subjects who continue treatment beyond progression, the BOR should be determined based on response designations recorded up to the time of the initial RECIST 1.1-defined progression.

Tumor response assessments will be performed every 8 weeks (± 1 week) after randomization during the first year and every 12 weeks (± 1 week) thereafter until investigator-assessed progression or treatment discontinuation, whichever occurs later.

8.3.2.2 Progression-Free Survival

Progression-free survival (PFS) is defined as the time from randomization to the date of the first documented tumor progression as determined by the investigator (per RECIST 1.1 criteria or clinical) or death due to any cause whichever occurs first. Subjects who die without a reported prior progression will be considered to have progressed on the date of their death. Subjects who did not progress or die will be censored on the date of their last evaluable tumor assessment. Subjects who did not have any on-study tumor assessments and did not die will be censored on the date they were randomized. Subjects who received any subsequent anti-cancer therapy without a prior reported progression will be censored at the last evaluable tumor assessment prior to initiation of the subsequent anti-cancer therapy.

Progression will be assessed by CT or MRI every 8 weeks (± 1 week) during the first year and every 12 weeks (± 1 week) thereafter, until investigator-assessed progression or treatment discontinuation, whichever occurs later.

8.3.2.3 Duration of Objective Response

Duration of objective response is defined as the time from first response (CR or PR) to the date of the first documented tumor progression as determined by the investigator using RECIST 1.1 criteria or death due to any cause, whichever occurs first. For subjects who neither progress nor die, the duration of objective response will be censored at the same time they were censored for the primary definition of PFS. This endpoint will only be evaluated in subjects with objective response of CR or PR. Tumor response assessments will be performed every 8 weeks (± 1 week) during the first year and every 12 weeks (± 1 week) thereafter until investigator-assessed progression or treatment discontinuation, whichever occurs later.

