5.4.11 Best Overall Response: All Time Points

The best overall response (BOR) is determined once all the data for the subject is known. BOR is defined as the best response designation, as determined by the investigator, recorded between the date of randomization and the date of objectively documented progression per RECIST 1.1 or the date of subsequent anti-cancer therapy, whichever occurs first. For subjects without documented progression or subsequent anti-cancer therapy, all available response designations will contribute to the BOR determination. For subjects who continue treatment beyond progression, the BOR should be determined based on response designations recorded up to the time of the initial RECIST 1.1-defined progression. The subject's BOR assignment will depend on the findings of both target and non-target disease and will also take into consideration the appearance of new lesions.

When SD is believed to be best response, it must also meet the protocol specified minimum time from baseline. If the minimum time is not met when SD is otherwise the best time point response, the subject's best response depends on the subsequent assessments. For example, a

subject who has SD at first assessment, PD at second and does not meet minimum duration for SD, will have a best response of PD. The same subject lost to follow-up after the first SD assessment would be considered not evaluable.

For purposes of this study, the minimum duration between baseline and first on-study scan in order to determine best response of SD is 7 weeks.

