5.4.12 Duration of Response

5.4.12.1 Duration of Overall Response

The duration of overall response is measured from the time measurement criteria are first met for CR/PR (whichever is first recorded) until the first date that progressive disease is objectively documented (taking as reference for progressive disease the smallest measurements recorded on study).

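### Duration of response borrows the PFS censoring date only for event-free responders, so censoring of a responder who switches therapy before progression depends on what happens afterwards

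*Protocol*

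**What the plan says.** Section 8.3.2.3 runs DOR from first response to "the date of the first documented tumor progression as determined by the investigator using RECIST 1.1 criteria or death due to any cause". It makes no exception for events after a change of therapy. Its only censoring rule is "For subjects who neither progress nor die, the duration of objective response will be censored at the same time they were censored" under the primary PFS definition.

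Section 8.3.2.2 has two separate censoring rules for PFS. One covers subjects without progression or death. The other covers subsequent therapy: "Subjects who received any subsequent anti-cancer therapy without a prior reported progression will be censored at the last evaluable tumor assessment prior" to its start. The second rule does not depend on what happens later.

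Section 5.4.12.1 describes DOR again. It runs "until the first date that progressive disease is objectively documented" and is also silent on subsequent therapy.

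Section 8.4.2.2 estimates DOR by Kaplan-Meier in each arm, in responders only, with a median and confidence interval and no between-arm test.

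**The concern.** Kaplan-Meier needs censoring that carries no information about the subject's later course. Under 8.3.2.3, whether a switching responder is censored at the pre-switch scan or followed past it is decided by whether an event is later seen. Post-switch events are kept and post-switch event-free time is thrown away. That is neither a rule that ignores subsequent therapy nor one that censors at it.

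DOR is what gives clinical meaning to ORR, the first key secondary endpoint. As written, some durations would include time on a different drug, and a subject censored early for PFS could be a late event for DOR.

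**Working it through.** The documents give no figure for DOR, so there is none to reproduce. The check is a side-by-side reading, one worked example, a count of expected responders, and an illustration of direction.

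**1. Are later events recorded?** Yes. The Follow-Up Phase in section 3.1 and Table 5.1-4 continue scans until progression in subjects who stop study drug for other reasons, and do not end them at a new therapy. Survival and subsequent therapy are followed every 3 months.

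**2. Two responders who differ only after the switch** (illustrative dates). Both respond at week 8, have a last evaluable scan before the switch at week 16, and start a new agent at week 20 without progression. Subject A progresses at week 56, a scheduled scan in Tables 5.1-2 and 5.1-3. Subject B is event-free at cut-off.

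| | PFS (8.3.2.2) | DOR (8.3.2.3 as written) |
|---|---|---|
| A | censored, week 16 | event at 56 − 8 = 48 weeks |
| B | censored, week 16 | censored at 16 − 8 = 8 weeks |

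Of A's 48 weeks, 56 − 20 = 36 fall after the new agent began. Under the PFS rule A would also be censored at 8 weeks. The 48 and the 8 should not be compared as durations, since one is an event time and the other a censoring time.

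**3. Expected responders.** 822 / 2 = 411 per arm.
- Everolimus, at the 2% response rate in section 1.4.3: 411 × 0.02 = 8.2, so one such subject is 1 / 8.2, about 12% of that arm's DOR data.
- Nivolumab, at 24% to 31% (section 1.4.5.2): 411 × 0.24 = 99 to 411 × 0.31 = 127. These rates come from 17 and 16 subjects at 1 and 10 mg/kg, not at the trial dose.

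The documents give no rate of switching before progression. If 5% to 15% of nivolumab responders switched (assumption), that is 0.05 × 99 = 5 to 0.15 × 127 = 19 subjects. This is an upper bound, because only switchers with a later event are affected.

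**4. Direction of the effect on the median.** All inputs here are assumed. True median DOR is 12 months with exponential times.
- *Switch time uniform between response and the progression that would have occurred.* With 5% to 30% switching, a median of 6 to 18 months from switch to later event, and cut-off 10 to 30 months after response, the median was 12.0 to 13.6 months under the literal rule and 12.3 to 15.1 months with PFS-type censoring. The literal rule was shorter in every scenario. This switching pattern itself pushes the censored estimate above 12, so the set shows direction and not which rule is closer to the truth.
- *A second set of assumptions*, with 10% or 30% switching, a post-switch median of 6 to 24 months, and cut-off at 24 or 40 months. The literal rule gave 10.9 to 12.2 months and PFS-type censoring 11.9 to 12.1. The literal median was longer, by at most 0.2 months, only with a 40-month cut-off and a long post-switch median (up to twice the on-drug median). With 10% switching the two differed by at most 0.4 months.

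The reason is that switchers who stay event-free leave the risk set early, while those who fail remain and add events.

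**The case against.** The strongest defence is that alignment was intended. Section 8.3.2.3 refers to the primary PFS definition, so a subject without a PFS event could be meant to take the PFS censoring date. PFS has an overlap of its own: a switcher who later dies fits both the death rule and the subsequent-therapy rule, and a reader resolves that sensibly. Order of precedence is often left to the statistical analysis plan, which is not at hand.

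The point about intent stands and shapes the fix. It does not remove the defect. Section 8.3.2.2 has an explicit subsequent-therapy sentence in addition to its rule for event-free subjects. Section 8.3.2.3 restates only the event-free condition, so a programmer following it would count the later event.

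Three stronger readings are tempting and are not supported.
- *DOR is overestimated.* Individual durations do include time on the next drug, but the documents give no post-switch hazard, and the median tends to move the other way.
- *DOR contradicts best overall response*, which stops at "the date of subsequent therapy, whichever occurs first". That cut-off decides which assessments can establish a response. It does not define when a response ends.
- *A known number of durations is affected.* The 5 to 19 above rests on an assumed switching rate and is an upper bound.

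It is also true that nothing inferential depends on DOR.

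**Conclusion.** The point holds on the stated wording. DOR censoring for responders who switch before progression depends on their later outcome, which makes it informative and inconsistent with PFS for the same subject. The direction of the effect on the median is not fixed by the documents.

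Severity is minor. DOR is descriptive and lies outside the OS-ORR-PFS hierarchy in section 8.4.2, so no alpha, power or primary conclusion changes. The number affected is unknown. At the rates quoted in the protocol, one case is about 12% of the expected everolimus responders and about 1% of the nivolumab responders (1 / 127 to 1 / 99). The conclusion assumes that 8.3.2.3 is followed as written; an analysis plan that already applies the PFS rule to all responders would settle it.

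**What to change.** Add to section 8.3.2.3: *Responders who begin another anti-cancer therapy with no progression reported beforehand are censored at their final evaluable scan before it starts, whatever happens afterwards, as for PFS.* Cross-refer to it from 5.4.12.1.

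Section 3.1 already treats the interim results as the final primary analysis, so label the change as a clarification that aligns DOR with PFS, and report the literal-rule result as a sensitivity analysis.

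When making the edit, also state how clinical progression is handled. PFS counts progression "as determined by the investigator (per RECIST 1.1 criteria or clinical) or death due to any cause whichever occurs first", whereas DOR names RECIST 1.1 only. A responder with clinical progression alone before a switch has a PFS event and so no PFS censoring date to borrow.

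Cost: one sentence and a small derivation change, with no new data. There will be fewer DOR events and somewhat less precision, and the median may move in either direction.

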8.3.2.4 Safety

Safety will be analyzed through the incidence of adverse events, serious adverse events and specific laboratory abnormalities (worst grade) in each treatment arm. Toxicities will be graded using the National Cancer Institute (NCI) Common Terminology Criteria for Adverse Events (CTCAE) version 4.0.

Adverse event assessment is performed on an ongoing basis while on treatment and for up to 100 days after the last dose of study drug (ie, during the X follow-up visits).

Laboratory tests are performed at baseline, on Day 1 of each cycle (within 72 hours prior to dose for all cycles except 1 (see [Table 5.1-2](#)), and at the first visit in follow-up. Tests at second visit in follow-up will be repeated if study drug related toxicity persists.

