- Subjects on nivolumab are re-dosed every 2 weeks with allowances for delay up to a maximum of 6 weeks from last dose (see [Sections 4.3.1.1](#) and [4.3.3.1](#)). Subjects on everolimus will continue daily oral dosing with allowances for delay up to a maximum of 6 weeks from last dose (see [Sections 4.3.1.2](#) and [4.3.3.2](#)). Subjects on both arms adhere to the same 4-week cycle length, with nivolumab arm (Arm A) subjects receiving 2 doses within the cycle.
- Treated subjects will be evaluated for response according to the RECIST 1.1 guidelines beginning 8 weeks from randomization (± 1 week) and continuing every 8 weeks (± 1 week) for the first 12 months from randomization, and then every 12 weeks (± 1 week) until disease progression or end of therapy, whichever occurs later.
- ePRO instruments will be completed according to [Table 5.1-2](#) & [Table 5.1-3](#). For subjects in the nivolumab extension phase, PRO assessments will be done according to the schedule in [Table 5.1-7](#) and [Table 5.1-8](#).
- This phase ends when the subject is discontinued from study therapy. For a complete list of reasons for treatment discontinuation, see [Section 3.5](#).

Follow-Up Phase:

- Begins when the decision to discontinue a subject from study therapy is made (no further treatment with study therapy).
- Two X follow-up visits include PK/immunogenicity samples only for subjects who received nivolumab (Arm A). Subjects in the nivolumab extension phase will have XX follow-up visits and will not provide PK and immunogenicity samples.
- Subjects that discontinue treatment for reasons other than disease progression will continue to have tumor assessments beginning 8 weeks from randomization (± 1 week) and continuing every 8 weeks (± 1 week) for the first 12 months from randomization and every 12 weeks (± 1 week) thereafter until disease progression is documented.
- Subjects will be followed for drug-related toxicities until these toxicities resolve, return to baseline, or are deemed irreversible.
- Subjects will be followed every 3 months for survival, to include subsequent anti-cancer therapy.
- ePRO instruments will be completed according to [Table 5.1-4](#).

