Patient-Reported Outcome Measurements		X	After randomization and prior to first dose: FKSI-DRS and EQ-5D (Use Cycle 1 visit on ePRO tablet for this visit)

^a All testing listed to be performed within 30 days prior to randomization, unless otherwise specified
Note: Screening period is not limited to 30 days, provided testing is performed within time frames noted.

Table 5.1-2: On-Study Procedural Outline Arm A- Nivolumab (BMS-936558)				
Procedure	Each Cycle Day 1	2nd Dose of Cycle	Q 8 wks from Randomization	Notes
Safety Assessments				
Targeted assessments	X			Except Cycle 1. Assessments within 48 hrs of dosing to include: Targeted physical exam, performance status and weight. Oxygen saturation by pulse oximetry at rest and after exertion (Section 5.3).
Adverse Events Assessment	X	X		eSAEs should be approved in TAO by Investigator within 4 days from entry.
Concomitant Medications	X	X		Note: Immunosuppressive agents are recorded on a separate log page
Laboratory Tests	X			Cycle 2 and beyond: (within 72 hrs of dosing) CBC w/differential, LFTs, BUN or serum urea, creatinine. Even cycles only (within 72 hours of dosing): Fasting serum lipids profile (total cholesterol, triglycerides, LDL, and HDL), fasting glucose, and TSH (See Section 5.3).
		X		LFTS only (within 72 hours of dosing)
Pregnancy Test	X			For WOCBP Serum or urine (Note: perform q6 weeks if cycle start is delayed)
Study Samples				PK, Immunogenicity, soluble factors, miRNA, peripheral blood RNA and PBMC. See Table 5.1-5 and Table 5.1-6 for schedule of samples
Efficacy Assessments				
Tumor Assessments			X	By methods used at baseline. Tumor assessments at week 8, 16, 24, 32, 40, 48, and 56 (± 1 wk) from randomization, then every 12 wks (± 1 wk) until disease progression is documented or treatment is discontinued, whichever occurs later.

Table 5.1-2: On-Study Procedural Outline Arm A- Nivolumab (BMS-936558)				
Procedure	Each Cycle Day 1	2nd Dose of Cycle	Q 8 wks from Randomization	Notes
Clinical Drug				
Administer Study Treatment	X	X		Record study drug infusion start and stop times for nivolumab (Arm A). Doses of nivolumab should not be given less than 12 days from the previous dose. If the 2nd dose cannot be given within a 28 day window, it will be omitted and the next dose received will be Day 1 of the next cycle.
Other				
Patient-Reported Outcome Measurements	X			Prior to any study-related procedures: FKSI-DRS and EQ-5D
Health Resource Utilization	X			Except cycle 1. (Section 5.8.1)

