Table 5.1-3: On-Study Procedural Outline Arm B- Everolimus			
Procedure	Each Cycle Q 4 Weeks Day 1	Q 8 wks from Randomization	Notes
Safety Assessments			
Targeted assessments	X		Except Cycle 1. Assessments within 48 hrs of dosing to include: Targeted physical exam, performance status and weight. Oxygen saturation by pulse oximetry at rest and after exertion (Section 5.3).
Adverse Events Assessment	X		eSAEs should be approved in TAO by Investigator within 4 days from entry.
Concomitant Medications	X		Note: Immunosuppressive agents are recorded on a separate log page
Laboratory Tests	X		Cycle 2 and beyond: (within 72 hrs prior to each new cycle) CBC w/differential, LFTs, BUN or serum urea, creatinine. Even cycles only (within 72 hours prior to each new cycle): Fasting serum lipids profile (total cholesterol, triglycerides, LDL, and HDL), fasting glucose, and TSH (See Section 5.3).
Pregnancy Test	X		For WOCBP Serum or urine (Note: perform q6 weeks if cycle start is delayed)
Efficacy Assessments			
Tumor Assessments		X	By methods used at baseline. Tumor assessments at week 8, 16, 24, 32, 40, 48, and 56 (± 1 wk) from randomization, then every 12 wks (± 1 wk) until disease progression is documented or treatment is discontinued, whichever occurs later.
Clinical Drug			
Administer Study Treatment	X		First dose of study medication must be administered within 3 working days of Randomization
Study Samples			Soluble factors, miRNA, peripheral blood RNA, PBMC See Table 5.1-5 and Table 5.1-6 for schedule of samples
Other			
Patient-Reported Outcome Measurements	X		Prior to any study-related procedures: FKSI-DRS and EQ-5D
Health Resource Utilization	X		Except cycle 1. (Section 5.8.1)

Table 5.1-4: Follow-Up Assessments (CA209025) - ALL Subjects			
Procedure	X or XX, Follow-Up Visit 1+ 2^a	Y or YY, Survival Follow-Up Visits^b	Notes
Safety Assessments			
Targeted Physical Examination	X		To assess for potential late emergent study drug related issues
Adverse Events Assessment	X		All new and continuing adverse events need to be documented and followed until 100 days after last dose (X02 or XX02 visit). If drug related events continue at second follow-up visit they need to be followed to resolution or until they are deemed irreversible by the investigator. eSAEs should be approved in TAO by Investigator within 4 days from entry.
Concomitant Medications	X		

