Performance status and body weight should be assessed at each new cycle visit. Vital signs should also be taken as per institutional standard of care prior to, during, and after the infusion of nivolumab. Oxygen saturation by pulse oximetry at rest and after exertion should be assessed prior to each new dosing of study medication. The start and stop time of the nivolumab infusion are to be documented. Some of the previously referred to assessments may not be captured as data in the eCRF. They are intended to be used as safety monitoring by the treating physician.

If there are any new or worsening clinically significant changes since the last exam, report changes on the appropriate non-serious or serious adverse event page.

On-study labs should be done within 72 hours prior to the next new cycle (except 1) to include: CBC w/ differential, LFTs, BUN or serum urea, creatinine. For subjects on the nivolumab arm (Arm A), LFTs should also be assessed prior to the 2nd dose of each cycle. The results of these labs should be reviewed prior to dosing.

In addition, for subjects on both treatment Arms A and B, the following tests will be assessed every even cycle (2, 4, etc): serum lipids profile (total cholesterol, triglycerides, LDL, and HDL) fasting glucose, and TSH. If TSH is abnormal, free T3 and free T4 should be assessed.

Additional measures including non-study required laboratory tests should be performed as clinically indicated.

Laboratory toxicities (eg, suspected drug-induced liver enzyme elevations) will be monitored during the follow-up phase with local labs until all study drug related toxicities resolve, return to baseline, or are deemed irreversible.

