8.4.3 Safety Analyses

Summary tables will be presented on safety parameters for each treatment arm. Toxicity rates (worst CTCAE grade per subject) of adverse events and specific laboratory tests will be tabulated.

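### Section 8.3.2.4 omits the mid-cycle liver tests drawn on nivolumab only, so worst-grade liver abnormalities are ascertained unequally and the descriptive between-arm contrast can be biased against nivolumab

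*Protocol*

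**What the plan says.** Section 8.3.2.4 defines the safety endpoint partly through "specific laboratory abnormalities (worst grade) in each treatment arm". On timing it says "Laboratory tests are performed at baseline, on Day 1 of each cycle", then adds the first follow-up visit, with a repeat at the second if drug-related toxicity persists. Its only schedule reference is Table 5.1-2, the on-study table for nivolumab (Arm A).

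The schedules themselves differ by arm:

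- **Nivolumab.** Section 5.3 states: "For subjects on the nivolumab arm (Arm A), LFTs should also be assessed prior to the 2nd dose of each cycle". Table 5.1-2 carries the same draw in its second-dose column, in addition to the Day 1 panel.
- **Everolimus.** Table 5.1-3 has one entry per cycle: "Cycle 2 and beyond: (within 72 hrs prior to each new cycle) CBC w/differential, LFTs, BUN or serum urea, creatinine". It has no mid-cycle draw.
- **Cycle length.** Section 3.1: "Subjects on both arms adhere to the same 4-week cycle length, with nivolumab arm (Arm A) subjects receiving 2 doses within the cycle".

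Section 8.4.3 fixes the summary: "Toxicity rates (worst CTCAE grade per subject) of adverse events and specific laboratory tests will be tabulated". It does not restrict the tables to common time points or allow for the number of tests.

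**The concern.** A worst grade per subject is a maximum over that subject's samples. If one arm is sampled every 2 weeks and the other every 4, two arms with the same true hepatic risk need not show the same observed rate. An elevation that rises and resolves between two Day 1 visits can be seen on nivolumab and missed on everolimus.

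A secondary objective in Section 1.3.2 is the safety and tolerability of nivolumab vs everolimus, and Section 4.3 lists hepatotoxicity among the events with their own management guideline. Readers will therefore set the two hepatic columns side by side. Someone working from Section 8 alone would not learn that the columns rest on different sampling.

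**Working it through.** The protocol gives no liver-abnormality rate and no duration of elevation, so there is no stated figure to reproduce. The check counts scheduled samples and asks what an identical true process would look like in each arm.

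**1. Scheduled on-treatment LFTs after baseline.** With W weeks on treatment, nivolumab has W/2 and everolimus W/4 (Tables 5.1-2 and 5.1-3, 4-week cycles).

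| Weeks | Nivolumab | Everolimus |
|---|---|---|
| 8 | 4 | 2 |
| 16 | 8 | 4 |
| 24 | 12 | 6 |
| 52 | 26 | 13 |

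**2. One episode of fixed duration D days (assumed), onset uniform over the sampling interval.** The chance that a scheduled sample catches it is min(1, D/14) on nivolumab and min(1, D/28) on everolimus.

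| D (days) | Nivolumab | Everolimus | Ratio |
|---|---|---|---|
| 7 | 50% | 25% | 2.0 |
| 14 | 100% | 50% | 2.0 |
| 21 | 100% | 75% | 1.33 |
| 28 or more | 100% | 100% | 1.0 |

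**3. Exponential duration with mean m weeks (assumed).** Detection at interval L is (m/L)(1 − exp(−L/m)). The ratio for L = 2 against L = 4 reduces to 2/(1 + exp(−2/m)). For m = 1, 2, 3, 4 and 8 weeks this is 1.76, 1.46, 1.32, 1.24 and 1.12. With a true incidence of 10% and m = 2, the observed rates are 10% × 0.632 = 6.3% on nivolumab and 10% × 0.432 = 4.3% on everolimus.

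**4. Simulation of true episodes.** This used 40,000 subjects, 24 weeks, a Poisson mean of 0.15 episodes per subject (true incidence about 14%) and fixed durations. Nivolumab against everolimus:

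- 7 days: 7.2% vs 3.7% (ratio 1.93)
- 14 days: 14.2% vs 7.4% (1.91)
- 21 days: 13.6% vs 10.5% (1.29)
- 28 days: 13.9% vs 13.9% (1.00)

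The nivolumab rate never exceeded the true incidence. The gap comes from episodes missed on everolimus.

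**5. Isolated single abnormal values.** With an independent chance p per test (assumed), the rate is 1 − (1 − p)^n. Over 24 weeks (n = 12 vs 6), p = 1% gives 11.4% vs 5.9% (1.94), and p = 5% gives 46.0% vs 26.5% (1.74).

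**6. Common time points.** If only draws scheduled in both arms are used, the count over 24 weeks is 6 vs 6. The detection ratio under an identical process is then 1.0 for any duration, given equal time on treatment.

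**The case against.** - **The reference already covers it.** Section 8.3.2.4 points to Table 5.1-2, which lists the mid-cycle LFT, and Section 5.3 states the difference between arms openly. This stands in part. A reader might infer that Section 8 asserts equal testing, or contradicts Section 5; it does neither. It is an incomplete summary that cites one arm's table.
- **Nivolumab is nearer the truth.** For true episodes this is right: more sampling finds more of what is there, and everolimus is the under-detected arm. The contrast between arms is still uneven.
- **Scheduled tests are not all tests.** Section 5.3 adds: "Additional measures including non-study required laboratory tests should be performed as clinically indicated". Section 4.3 also drops a second nivolumab dose that cannot be given within the 28-day period, and the draw tied to it may go too. Both narrow the gap by an unknown amount, so the 2:1 count of scheduled tests is an upper bound.
- **The tables are descriptive, and the SAP may choose the samples.** No between-arm test of laboratory rates is planned, and the SAP is not shown. That limits the weight of the point. The incomplete timing sentence and the worst-grade summary are, however, protocol text.
- **A Day 1 table has its own bias.** Mid-cycle results are reviewed before dosing (Section 5.3), and drug-related AST, ALT or bilirubin elevations can delay nivolumab (Section 4.3.1.1). Day 1 values on nivolumab can therefore already reflect action taken on mid-cycle results. This stands, and it is why such a table must not replace the all-samples table.

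**Conclusion.** The point holds as one of unequal ascertainment. Section 8.3.2.4 is incomplete, and the worst-grade liver summary takes a maximum over up to twice as many scheduled samples on nivolumab. Under an identical true process the ratio of scheduled-sample detection runs from 1.0 (episodes of 28 days or more) to about 2.0 (14 days or less). The durations are assumptions, and the calculation ignores unscheduled tests and omitted second doses. Scheduled sampling alone cannot push the ratio below 1, so any bias in the contrast runs against nivolumab.

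Two stronger readings are tempting and are not supported:

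- A reader might infer that nivolumab's liver rate is necessarily inflated. For true episodes it is not raised above the truth; only isolated or spurious values would do that, and the gap disappears for long-lasting abnormalities.
- A reader might infer that the mid-cycle LFTs in the extension phase (Table 5.1-8) distort the everolimus column. Nothing in the protocol says extension-phase laboratory data are pooled into Arm B.

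The consequence is confined to descriptive hepatic laboratory rates. OS, ORR, PFS and the type I error are untouched. This is a low-cost improvement to the safety reporting.

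**What to change.** 1. In Section 8.3.2.4, state that LFTs are also drawn before the second dose of each cycle in Arm A only, and cite Table 5.1-3 alongside Table 5.1-2.
2. In Section 8.4.3, keep the all-samples worst-grade table as the main safety summary.
3. Add a supplementary worst-grade table for AST, ALT, bilirubin and alkaline phosphatase, limited to time points scheduled in both arms: baseline, Day 1 of each cycle and follow-up visit 1. It is to be read for the between-arm contrast.
4. Footnote the supplementary table with its two limits: it omits true mid-cycle abnormalities on nivolumab, and Day 1 values on nivolumab may already reflect action taken on mid-cycle results.

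The cost is a text correction, one extra table and its footnote. No additional data are needed, and the clinical monitoring schedule does not change.
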